8.2. Medications to be Used with Caution

8.2.1 CYP3A- Inhibitors/Inducers

Ibrutinib is metabolized primarily by CYP3A. Concomitant use of ibrutinib and drugs that strongly or moderately inhibit CYP3A can increase ibrutinib exposure, and strong CYP3A inhibitors should be avoided.

Strong CYP3A inhibitors

Co-administration of ketoconazole, a strong CYP3A inhibitor, in 18 healthy subjects, increased exposure (Cmax and AUClast) of ibrutinib by 29- and 24-fold, respectively. In a dedicated drug-drug interaction study in subjects with B-cell malignancies, co-administration of voriconazole increased Cmax and AUC by 6.7-fold and 5.7-fold,

^{**} If further reduction is needed due to non-hepatic toxicity, ibrutinib should be held until resolution.

respectively. In clinical studies, the maximal observed ibrutinib exposure (AUC) was ≤2-fold in 37 subjects treated with mild and/or moderate CYP3A inhibitors when compared with the ibrutinib exposure in 76 subjects not treated concomitantly with CYP3A inhibitors. Clinical safety data in 66 subjects treated with moderate (n=47) or strong CYP3A inhibitors (n=19) did not reveal meaningful increases in toxicities. Voriconazole and posaconazole can be used concomitantly with ibrutinib. All other strong inhibitors of CYP3A (e.g., ketoconazole, indinavir, nelfinavir, ritonavir, saquinavir, clarithromycin, telithromycin, itraconazole, nefazodone, and cobicistat) should be avoided, and an alternative with less CYP3A inhibitory potential should be considered. If the benefit outweighs the risk and a strong CYP3A inhibitor must be used, please discuss recommendations for dosing with the PI and document the discussion in the medical record.

Moderate and mild CYP3A inhibitors

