In subjects with B-cell malignancies, co-administration of the CYP3A inhibitor erythromycin increased Cmax and AUC by 3.4-fold and 3.0-fold, respectively. If a moderate CYP3A inhibitor (e.g., fluconazole, erythromycin, amprenavir, aprepitant, atazanavir, ciprofloxacin, crizotinib, diltiazem, fosamprenavir, imatinib, verapamil, amiodarone, dronedarone) is indicated, reduce the ibrutinib dose to 280 mg once daily for the duration of the inhibitor use or as per recommended dose modifications described in the specific clinical study protocol. In subjects with cGVHD, if a co-administration of voriconazole and posaconazole (at doses less than or equal to suspension 200 mg twice daily) is indicated, reduce the ibrutinib dose to 280 mg once daily. If a co-administration of higher doses of posaconazole (i.e., suspension 200 mg three times daily or 400 mg twice daily; IV injection 300 mg once daily; delayed-release tablets 300 mg once daily) is indicated, reduce the ibrutinib dose to 140 mg once daily. No ibrutinib dose modifications for moderate inhibitors are required for cGVHD subjects. Follow the specific instructions described in the clinical study protocol. No dose adjustment is required in combination with mild inhibitors. Monitor subjects closely for toxicity and follow dose modification guidance as needed. Avoid grapefruit and Seville oranges during ibrutinib treatment as these contain moderate inhibitors of CYP3A.

Strong CYP3A inducers.

Administration of ibrutinib with strong inducers of CYP3A decreases ibrutinib plasma concentrations by up to 90%.

Avoid concomitant use of strong CYP3A inducers (e.g. carbamazepine, rifampin, phenytoin and St. John's Wort). Consider alternative agents with less CYP3A induction.

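### Voriconazole and posaconazole are permitted, but the 280 mg ibrutinib dose that goes with them is written for cGVHD subjects, so a CLL/SLL patient on voriconazole has no stated dose reduction

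*Combined protocol and SAP*

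**What the plan says.** The trial enrols patients with CLL/SLL (section 4.1) and gives ibrutinib at 420 mg daily (section 5.2).

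Under its strong-inhibitor heading, section 8.2.1 reports that in subjects with B-cell malignancies "co-administration of voriconazole increased Cmax and AUC by 6.7-fold and 5.7-fold", respectively. It then states: "Voriconazole and posaconazole can be used concomitantly with ibrutinib". Other strong inhibitors are to be avoided. The paragraph closes with a fallback for cases where the benefit outweighs the risk and "a strong CYP3A inhibitor must be used, please discuss recommendations for dosing with the PI". The same paragraph offers a safety statement: "Clinical safety data in 66 subjects treated with moderate (n=47) or strong CYP3A inhibitors (n=19) did not reveal meaningful increases in toxicities".

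Under its heading for moderate and mild inhibitors, section 8.2.1 reports, again in B-cell malignancies, that "co-administration of the CYP3A inhibitor erythromycin increased Cmax and AUC by 3.4-fold and 3.0-fold", respectively. It lowers ibrutinib to 280 mg while a moderate inhibitor is taken. The 280 mg dose for voriconazole and lower-dose posaconazole follows, in a sentence opening "In subjects with cGVHD, if a co-administration of voriconazole and posaconazole". A further sentence gives 140 mg with higher posaconazole doses and names no population. The text then says cGVHD subjects need no change for moderate inhibitors, and adds "Follow the specific instructions described in the clinical study protocol" and "Monitor subjects closely for toxicity and follow dose modification guidance as needed".

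Section 8.3 bans chronic strong CYP3A inhibitors but exempts voriconazole and posaconazole, referring back to 8.2.1. Section 6.0 carries the same ban on chronic use with no exemption.

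**The concern.** The protocol permits two strong inhibitors and sends the reader to 8.2.1 for the terms. For voriconazole and lower-dose posaconazole, the dose found there belongs to a different disease population. The instruction to consult the clinical study protocol does not help, because this document is that protocol.

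Taken literally, a clinician treating a CLL/SLL patient has a number for erythromycin or fluconazole but none for voriconazole, whose reported effect on exposure is larger. These patients have no indication for treatment under the IWCLL criteria (section 4.1), so tolerance for avoidable toxicity should be low. Section 6.6 describes fatal bleeding and arrhythmia events on ibrutinib. The stake is patient safety and consistent dosing between patients, not the statistical analysis.

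**Working it through.** The plan gives no figure of its own to reproduce on this point. The check is a comparison of the text, with one ratio.

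**Step 1. What dose applies to whom (section 8.2.1).**

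| Co-medication | Reported AUC effect | Ibrutinib dose stated | Population named |
|---|---|---|---|
| Moderate inhibitor, e.g. erythromycin or fluconazole | 3.0-fold (erythromycin) | 280 mg | None; cGVHD subjects are then excused |
| Voriconazole | 5.7-fold | 280 mg | cGVHD only |
| Posaconazole suspension up to 200 mg twice daily | Not given | 280 mg | cGVHD only |
| Posaconazole, higher doses | Not given | 140 mg | None in that sentence |
| Other strong inhibitors | 24-fold (ketoconazole, healthy subjects) | Avoid; otherwise PI discussion | None |

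For CLL/SLL, the voriconazole and lower-dose posaconazole rows have no applicable number.

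**Step 2. Does another section supply it?** Section 7.1 covers dose changes after an adverse reaction. Sections 7.2 to 7.4 cover toxicity and leukostasis, and section 7.5 covers hepatic impairment. None gives an ibrutinib dose for azole use. Section 7.0 lets the investigator depart from the toxicity guidance, without a number.

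**Step 3. Can the cGVHD dose simply be read across?** Not safely. The same paragraph treats the populations differently: moderate inhibitors lead to 280 mg in general but to no change in cGVHD. The cGVHD instructions are therefore not interchangeable with those for CLL/SLL.

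**Step 4. Size of the interaction.** For a common ibrutinib dose D:

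AUC(D with voriconazole) / AUC(D with erythromycin) = [AUC(D) × 5.7] / [AUC(D) × 3.0] = 5.7 / 3.0 = 1.9

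For Cmax the same calculation gives 6.7 / 3.4 = 1.97, or about 2.0. The unboosted exposure at dose D cancels, so dose proportionality is not needed. The calculation assumes only that the two reported ratios apply at dose D and can be compared across their source studies.

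**Step 5. Permission.** Section 6.0 prohibits strong CYP3A inhibitors taken chronically. Section 8.3 prohibits the same class but lets voriconazole and posaconazole through. For chronic use of either drug, the two sections give opposite answers. For short courses they do not conflict.

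**The case against.** The best defence is that strong inhibitors are not left uncontrolled. Section 8.2.1 says they should be avoided and asks for a documented PI discussion when one must be used. That sentence sits under the strong-inhibitor heading and can be read to include these azoles, although it follows directly on a sentence about all the other strong inhibitors. This stands in part: there is a process, but it names no dose. Likewise, higher-dose posaconazole already has 140 mg, and the 280 mg rule for moderate inhibitors itself allows for protocol-specific alternatives. A reader might infer that the protocol is more lenient on strong inhibitors in general. It is not. The gap is a missing number for voriconazole and lower-dose posaconazole.

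A reader might also infer that patients will receive 420 mg with voriconazole, at nearly three times the exposure of the reduced erythromycin case: 5.7 / (280/420 × 3.0) = 2.85. No section directs that combination. The figure also needs AUC to be proportional to dose, whereas section 6.4 says only that exposure rose with dose and varied widely between subjects.

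The safety statement is real evidence on the other side. Its weight is limited: only 19 of the 66 subjects took strong inhibitors, and neither the drugs nor the ibrutinib doses are given. It would go too far to attach a power figure for a particular toxicity, since the text does not say which events were examined or for how long.

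On permission, section 6.0 is background text, its examples name no azole, and the specific exemption in 8.3 would normally prevail. That makes the conflict easy to resolve, but it is still there. Exclusion criterion 6 also lacks the exemption, and a reader might count it as a second contradiction. It can be read as applying at entry only, so the documents do not support that.

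**Conclusion.** The point holds as a patient-safety consistency correction. The protocol permits voriconazole and posaconazole, yet for a CLL/SLL patient on voriconazole or lower-dose posaconazole it states no numeric reduction from 420 mg. It does reduce to 280 mg for moderate inhibitors, and voriconazole raises AUC 1.9 times as much as erythromycin at a common dose. That ratio rests only on the two fold-changes printed in section 8.2.1. No interaction figure is given for posaconazole, so the size of its gap is not estimated.

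The documents do not derive a voriconazole dose below 280 mg. A reader might infer that 140 mg is the right one, but nothing in the text establishes it.

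The practical frequency is unknown and may be low. Section 8.1 permits antifungal prophylaxis, but section 5.1 does not list it among the recommended drugs. No effect on the 24-month CR/CRi analysis or other efficacy results is claimed.

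**What to change.** In section 8.2.1, replace the cGVHD wording with a rule for CLL/SLL:

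- While a patient takes voriconazole, or posaconazole suspension up to 200 mg twice daily, ibrutinib is no more than 280 mg once daily.
- With higher posaconazole doses, ibrutinib is 140 mg once daily.
- The documented PI discussion expressly applies to both azoles, and any voriconazole-related dose below 280 mg is set there.

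In section 6.0, add the voriconazole and posaconazole exception so that it matches section 8.3.

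The cost is a short text amendment, with no added procedures or patients. Section 15 requires amendments to go to the drug supplier for approval and then to the IRB. The downside is possible lower ibrutinib exposure, limited to the period of azole use.

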8.2.2 Antiplatelet Agents and Anticoagulants

Use ibrutinib with caution in subjects requiring anticoagulants or medications that inhibit platelet function. In an in vitro platelet function study, inhibitory effects of ibrutinib on collagen-induced platelet aggregation were observed. Supplements such as fish oil and vitamin E preparations should be avoided during treatment with ibrutinib. Bleeding events of any grade, including bruising and petechiae, occurred in subjects treated with ibrutinib. Subjects with congenital bleeding diathesis have not been studied. Ibrutinib should be held at least 3 to 7 days pre- and post-surgery depending upon the type of surgery and the risk of bleeding (see Section 8.4).

Subjects requiring the initiation of therapeutic anticoagulation therapy (e.g., atrial fibrillation) should be monitored closely for signs and symptoms of bleeding and the risks and benefits of continuing ibrutinib treatment should be considered.

8.3 Excluded concomitant therapy

Use of the following therapies is prohibited during the study:

- Any therapies intended for the treatment of lymphoma/leukemia whether FDAapproved or experimental (outside of this study)
- Radiotherapy (Note: Localized radiotherapy to an area not compromising bone marrow function is allowed)
- Steroid therapy for anti-neoplastic intent. Short courses (<=14days) of steroid treatment for non-cancer related medical reasons (e.g. joint inflammation, asthma exacerbation, rash, antiemetic use and infusion reactions) at doses that do not exceed 100mg per day of prednisone or equivalent are permitted.
- Strong CYP3A inhibitors which would be taken chronically, with the exception of voriconazole and posaconazole, as outlined in section 8.2.1.
- Grapefruit, Seville oranges, Star fruit
- Strong CYP3A inducers (e.g. rifampin, rifabutin, phenytoin, carbamazepine, and St. John's Wort) are not recommended
- The use of warfarin is not allowed during this study

8.4 Guidelines for Ibrutinib Management with Surgeries or Procedure

Ibrutinib may increase risk of bleeding with invasive procedures or surgery. The following guidance should be applied to the use of ibrutinib in the perioperative period for subjects who require surgical intervention or an invasive procedure while receiving ibrutinib.

8.4.1 Minor Surgical Procedures

For minor procedures (such as a central line placement, needle biopsy, thoracentesis, or paracentesis) ibrutinib should be held for at least 3 days prior to the procedure and should not be restarted for at least 3 days after the procedure. For bone marrow biopsies that are performed while the subject is on ibrutinib, it is not necessary to hold ibrutinib for these procedures.

8.4.2 Major Surgical Procedures

For any surgery or invasive procedure requiring sutures or staples for closure, ibrutinib should be held at least 7 days prior to the intervention and should be held at least 7 days after the procedure and restarted at the discretion of the investigator when the surgical site is reasonably healed without sero-sanguineous drainage or the need for drainage tubes.

8.4.3 Emergency Procedures

For emergency procedures, ibrutinib should be held after the procedure until the surgical site is reasonably healed, or for at least 7 days after the urgent surgical procedure, whichever is longer.

9.0 PRETREATMENT EVALUATIONS

- Pretreatment evaluation will include a complete history and physical examination including vital signs, ECOG performance status, height and weight and recording of concurrent medications (within 30 days of the first dose)
- 2. Complete blood count (hemoglobin, white blood cell count, platelet count, white blood count differential) (within 30 days of the first dose)
- 3. Clinical laboratory evaluation will include serum sodium, potassium, calcium, BUN, creatinine, glucose, phosphorous, magnesium, albumin, total protein, alkaline phosphatase, total bilirubin, ALT, uric acid, LDH, β-2 microglobulin, immunoglobulins (within 30 days of the first dose)

- 4. Coagulation profile (PT, aPTT)
- 5. Immunologic evaluation (within 30 days of the first dose).
- 6. CLL prognostic markers, including CLL FISH panel, *IGHV* mutation status, ZAP-70, CD38, and CLL next generation sequencing panel (within 30 days of the first dose). This testing can be done either in peripheral blood or bone marrow. Retesting for *IGHV* mutation status and ZAP70 is not required if previously done at MDACC. Additionally, if CLL next generation sequencing panel and FISH has been performed within the past year at MDACC, these do not need to be repeated.
- 7. HIV Ab, Hepatitis C Ab, HBsAg, anti-HBcAb (within 30 days of the first dose)
- 8. Women of childbearing potential must have a negative serum or urine β-hCG pregnancy test result (within 7 days of the first dose)
- 9. 12-lead EKG (within 30 days of the first dose)
- 10. MUGA or Echocardiogram (within 30 days of the first dose)
- 11. Bone marrow aspiration and biopsy (within 90 days of the first dose if no intervening treatment for CLL given)
- 12. CT scan of the neck, chest, abdomen, and pelvis with IV and oral contrast, within 90 days of the first dose with no intervening treatment for CLL given. Patients with palpable cervical lymphadenopathy noted at screening physical examinations should have imaging of the neck included in their screening imaging studies and at subsequent time points for response assessment. Note: PET scan or MRI may be used instead of the CT scan imaging.
- 13. Immunologic evaluation. Peripheral blood samples will be taken to evaluate immune function and the relationship between immune function and outcome, as a research test.
- 14. Circulating tumor DNA analysis and sequencing of peripheral blood mononuclear cells will be done in [name]'s lab at Peter MacCallum Cancer Center, Melbourne, Australia, as a research test.

10.0 EVALUATION DURING THERAPY

Cycle	Screening/	1	2	3	6	9	12	18	24	At
	baseline(1)									progression
Day within cycle(2)	-30 to 1	28	28	28	28	28	28	28	28	
Informed consent(3)	Х									

Medical history(4)	Х	Х	X	X	X	X	X	X	X	Х
Physical examination including	Х				X		X	X	X	Х
vital signs(5)										
Concomitant medications(6)	Х									
Complete blood count with	Х	Х	X	X	X	X	X	X	X	Х
differential(7)										
Biochemistry(8)	Х	X	X	X	X	X	X	X	X	Х
CT scan(9)	Х				X		X		X	Х
Bone marrow examination and	Х				X		X		Х	Х
cytogenetics(10)										
ECG(11)	Х									
Echocardiogram(12)	Х									
Pregnancy test(13)	Х									
QOL evaluation(14)	Х						X		X	Х
Immunologic evaluation(15)	Х			X	X		X			Х
Circulating tumor DNA	Х	Х		X	X		X		X	Х
analysis(16)										

- (1) Screening period testing. All the above must be completed within 30 days of study enrolment, except where stated otherwise in section 9.0.
- (2) Evaluations within the first 3 cycles of therapy must take place within +/- 7 days of scheduled time. Evaluations during cycle 6-12 must take place within +/- 2 weeks of scheduled date. Evaluation during cycles 18-24 must take place within +/- 4 weeks of scheduled time.
- (3) Informed consent. All patients must take part in the informed consent process. During the consent process, the person obtaining consent must inform the patient of all elements of informed consent. Adequate time must be allowed for questions and for the patient to make a voluntary decision. No protocol-specific procedures are to be performed until the patient has signed and dated an Institutional Review Board (IRB)/Ethics Committee (EC)-approved informed consent form. Each patient's participation in the trial begins with the signing and dating of the informed consent form.

- (4) Medical history. Medical and surgical history and demographic information will be recorded. Medical and surgical history includes diagnoses, therapies, and medical and surgical treatments. A complete medical history will be obtained at screening/baseline, prior to first administration of study drug and at the end-of-treatment visit. At all other visits, the medical history taking can be focused to the needs of the patient but should pay particular attention to adverse events that are potentially related to ibrutinib, infections, and disease-related symptoms. During the CoVID19 epidemic, medical history may be obtained by the patient's M.D. Anderson Physician in a telephone or videoconference interview and documented in the chart.
- (5) Physical examination, including vital signs. Vital signs are temperature, pulse, respiratory rate, and blood pressure (when the patient is seated). A complete physical examination, including measurement of weight, must be performed at screening/baseline, prior to the first administration of study drug, and at the end-of-treatment Visit. Height need only be recorded at the initial visit. Following the screening/baseline physical examination, with the exception of the end-of-treatment Visit, all subsequent physical examinations can be focused to the individual needs of the individual patient. Given that, during the CoVID19 epidemic, many patients will not be able to come to M.D. Anderson, some assessments may be conducted remotely. Wherever possible, patients should have a physical exam at least every 6 months and, if unable to come to M.D. Anderson, this should be done by a local physician and the records obtained. If even this is not possible, the reasons for this should be documented in the patient's chart.
- (6) Concomitant medications. These will be recorded in the electronic medical record.
- (7) Complete blood count with differential. CBC with differential is defined as peripheral blood total white blood cell (WBC) count, hemoglobin, hematocrit, platelet count, absolute neutrophil count (ANC), and WBC differential, reported individually for each cell type. Hematologic assessments must be obtained at screening and at every subsequent assessment, as specified in the Schedule of Events, or more frequently as clinically indicated (e.g. to confirm loss of hematologic response as defined in section 9.1).
- (8) Biochemistry. Serum chemistry consists of a peripheral blood draw with the following assessments: include serum sodium, potassium, calcium, BUN, creatinine, glucose,

phosphorous, magnesium, albumin, total protein, alkaline phosphatase, total bilirubin, ALT, uric acid, LDH, β-2 microglobulin, immunoglobulins.

- (9) CT of the neck, chest, abdomen and pelvis will be performed for response evaluation. If PET/CT or MRI was performed pre-treatment, this should be performed instead of CT scan, if available. If patients achieve complete remission by CT criteria (see section 11.0), subsequent CT scans can be omitted, per investigator discretion.
- (10) Bone marrow examination with CLL FISH panel and flow cytometry will be performed pre-treatment and at 6, 12, and 24 months. Conventional stimulated metaphase karyotyping will be performed at baseline and at disease progression, using local protocols. Pre-treatment, CLL FISH panel need not be repeated if performed at MDACC within the past year.
- (11) ECG. ECG will be done prior to treatment, in the routine diagnostic lab and then as clinically indicated.
- (12) Echocardiogram. ECHO or MUGA will be performed at screening (within 2 weeks of starting treatment) and at end of treatment or at 2 years, whichever is soonest. If a patient has undergone ECHO or MUGA as standard of care prior to entering the study, the procedures will not have to be repeated if results are available and the procedures were performed within 28 days of study entry.
- (13) Pregnancy test. The pregnancy test must be a beta-human chorionic gonadotropin (β-HCG) test, using either urine or serum. Women who are not of childbearing potential (status post-hysterectomy, status post-bilateral oophorectomy, or postmenopausal [defined as amenorrhea for at least 12 months]) do not need to have the test performed. If the test is deemed necessary, it must be performed within 7 days preceding the commencement of study therapy and known to be negative. Women of childbearing potential at study commencement must also complete the pregnancy test at the End-of-Treatment Visit.
- (14) QOL evaluation. Quality of life will be evaluated using the FACIT-Fatigue and EQ-5D-5L questionnaires pre-treatment, at 12 months, 24 months and at disease progression.

- (15) Immunologic evaluation. Peripheral blood samples will be taken at baseline, 3, 6, 12 months and at disease progression, to evaluate immune function and the relationship between immune function and outcome. This will be done as a research test. Please note that, as a result of the CoVID19 epidemic, it may be impossible to obtain research lab draws. Missed research lab draws will not be considered as deviations.
- (16) Circulating tumor DNA analysis and sequencing of peripheral blood mononuclear cells will be done in [name]'s lab at Peter MacCallum Cancer Center, Melbourne, Australia pre-treatment and at 1, 3, 6, 12, 24 months and at disease progression. Please note that, as a result of the CoVID19 epidemic, it may be impossible to obtain research lab draws. Missed research lab draws will not be considered as deviations.

